5.3. Baseline Definition

For efficacy and safety analysis purpose, unless otherwise specified, the assessments collected at the randomization visit (ie, Day1 [Visit 2]) prior to dosing will serve as the baseline value. If the randomization visit value is not available, then the last measurement collected prior to randomization will serve as baseline.

5.4. Derived and Transformed Data

Change from baseline will be calculated as the post-baseline value minus the baseline value; a negative value will represent a decrease at the post-baseline visit. Percent change from baseline will be calculated as (change from baseline/baseline value × 100). If either the baseline or postbaseline value is missing, the change from baseline and/or percent change from baseline will also be missing. If the baseline value is equal to zero, the percent change from baseline will be missing.

5.5. Study Day

Study day will be calculated relative to the date of the first study treatment (Study Day 1) for dates on or after Day 1:

Study Day = Date of Interest – Date of Study Day 1 + 1

Study day will be calculated relative to Study Day 1 for dates before Day 1:

Study Day = Date of Interest – Date of Study Day 1

5.6. Visit Windows

Study day is calculated relative to the date of the Day 1 visit. For efficacy data analysis, the nominal visit number for each visit, including scheduled and early termination/end of study visits will be re-mapped based on the actual study day according to Table 1.

Table 1: Analysis Visit Windows for Efficacy Analysis

Scheduled Visit	Target Study Day	Analysis Window (Analysis Day Range)
Baseline	1	1
Day 29	29	2-43
Day 57	57	44+

For safety data analysis, the nominal visit number for each visit, including scheduled, unscheduled, repeated and early termination/end of study visits, will be re-mapped to an analysis visit according to Table 2: Analysis Visit Windows for Safety Analysis

.

Neurocrine Biosciences, Inc. Statistical Analysis Plan Study NBI-1065846-MDD2020 16August2023

Table 2: Analysis Visit Windows for Safety Analysis

Scheduled Visit	Target Study Day	Analysis Window (Analysis Day Range)
Baseline	1	1 prior to first dosing
Day 1 Post Baseline	1	1 post first dosing
Day 8	8	2-15
Day 22	22	16-25
Day 29	29	26-36
Day 43	43	37-50
Day 57	57	51-last dose day
Day 78	Last dose day+28	Last dose day+1-last dose day+42
Day 106	Last dose day+56	last dose day+43+

If multiple measurements occur within the same visit window after mapping, the measurement that is closest to the target study day will be used for the summary tables where one observation per visit is needed, unless otherwise specified. Where there are ties between the earlier and later observation within the visit window, the earlier observation will be used.

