8.2. Withdrawal from Study

If a subject prematurely withdraws from the study, the investigator will record the reason for withdrawal on the relevant eCRF. All subjects who withdraw from the study prematurely will be asked to have all ET assessments performed and, unless consent has been withdrawn, will be asked to come back for 2 safety follow-up visits at 4 and 8 weeks after last dose of study treatment. If a subject's last dose of study treatment was >8 weeks before the ET visit, the Safety Follow-Up visits are not needed. If a subject's last dose of study treatment was >3 weeks but <8 weeks before the ET visit, only the Week 16 Safety Follow-Up visit is needed (ie, only one Safety Follow-Up visit approximately 8 weeks after the last dose of study treatment is needed).

Reasons for withdrawal from study include, but are not limited to:

- Withdrawal by the subject
- AE
- Death
- Lost to follow-up
- Site terminated by Sponsor
- Study terminated by Sponsor
- Protocol deviation
- Investigator decision
- Sponsor decision

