Virtual Visit				X		X			
AE assessment	X	X	X	X	X	X	X	X	X
Concomitant medications	X	X	X	X	X	X	X	X	X
Schedule exit interview							X		

AE=adverse event; ; CGI-S= Clinical Global

Impression – Severity; C-SSRS=Columbia-Suicide Severity Rating Scale; DARS=Dimensional Anhedonia Rating Scale; ECG=electrocardiogram; ET=early termination; FSH=follicle-stimulating hormone; HAM-D17=Hamilton Depression Rating Scale-17; MADRS=Montgomery-Åsberg Depression Rating Scale; MGH-ATRQ=Massachusetts General Hospital - Antidepressant Treatment Response Questionnaire; MINI=Mini-International Neuropsychiatric Interview; PCRS=Placebo-Control Reminder Script;

PK=pharmacokinetics;

; SAFER= State versus Trait, Assessability, Face Validity, Ecological Validity,

Rule of Three P's; SHAPS=Snaith-Hamilton Pleasure Scale W=week

- ^a Subjects will undergo screening procedures that may be completed in 1 or more visits during the Screening Period of up to 4 weeks. Subjects may be rescreened once based on the clinical judgment of the investigator in collaboration with the sponsor or designee. The screening period may be extended by up to 14 days in extenuating circumstances in consultation with the Sponsor or designee.
- ^b Assessments on Day 1 should be performed prior to study treatment administration.
- ^c Subjects will return to the clinic approximately 4 and 8 weeks following their final dose for safety follow-up or 7 days (±2) for the ET visit assessments if the subject discontinues study treatment or withdraws consent to participate in the study.
- d After consent is obtained, the registry database check should be performed as early as possible at the screening visit to avoid unnecessary procedures.
- ^e Height will be collected at screening only.
- f Triplicate 12-lead ECGs will be performed (at least 1 minute apart and within 15 minutes) after the subject has rested supine for at least 5 minutes on screening, Day 1, Day 29, and Day 57 or ET visit. On Day 1 and Day 29, ECGs will be performed at predose and 2 hours postdose. ECGs are also needed on Day 78 and Day 106 if ECG(s) during the Treatment Period were abnormal.
- g Vital signs will be measured for the following: orthostatic systolic and diastolic blood pressure, orthostatic pulse rate, respiratory rate, and body temperature. The same method should be used to take body temperature throughout the study.

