7.3.2. Estimand

Consistent with the International Council for Harmonization of Technical Requirements for Pharmaceuticals for Human Use (ICH) E9 Addendum, the 4 attributes of the estimand in conjunction with the primary endpoint are:

- Population:
 - Subjects with a diagnosis of MDD who have been treated with antidepressant medication(s) and who continue to have anhedonia as defined by the study inclusion/exclusion criteria (Section 5 of the protocol).

Neurocrine Biosciences, Inc. Statistical Analysis Plan Study NBI-1065846-MDD2020 16August2023

- Endpoints:
 - Change from baseline in the DARS score at Day 57.
- Intercurrent events:
 - Subjects who discontinue study treatment prematurely or make changes to their background medications will continue to be followed per protocol, therefore the treatment policy strategy will be used to address intercurrent events.
- Summary measures:
 - Difference of means in change from baseline in the DARS score at Day 57 between NBI-1065846 and placebo.

All available assessments up to Day 57 will be used, regardless of occurrence of intercurrent events.

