7.4. Primary Efficacy Endpoint

The DARS is a dynamic scale that measures desire, motivation, effort and consummatory pleasure across hedonic domains. The DARS is a self-report questionnaire that measures anhedonia across 4 domains: hobbies/pastimes, food/drinks, social activities, and sensory experiences. The DARS is rated on a five-point Likert scale from 0 (not at all) to 4 (very much), higher values indicating less anhedonia. All items are summed up to a total score in the range of 0 to 68.

Descriptive statistics will be presented by treatment group for the DARS total score observed values, and changes from baseline at each visit. The primary endpoint will be analyzed using the Full Analysis Set by comparing NBI-1065846 and placebo using an Analysis of Covariance (ANCOVA) model. The model will include treatment group, illness severity (stratification factor), use of concomitant antidepressant medication(s) at time of randomization ([ie, yes vs no], covariate), and baseline DARS score (covariate).

Subjects who are missing DARS score at Day 57 will have their data imputed through a multiple imputation (MI) procedure. Missing data will be imputed for subjects in the NBI 1065846 treatment group using retrieved data (i.e., observed data from subjects who discontinued study drug) in that same treatment group, provided there is sufficient retrieved data. Otherwise, missing data will be imputed using observed data from subjects in the placebo treatment group, missing data will be imputed using observed data from subjects in the placebo treatment group. The details of imputation method are described below:

Step 1: For subjects with intermittent missing values, a monotone missingness pattern will be generated by imputing for the intermittent missing values using the Markov Chain Monte Carlo (MCMC) method, which assumes a multivariate normal distribution among all variables included in the imputation model. The MI procedure using SAS® software will be employed for this purpose and this first MI step is planned to be repeated 100 times, creating several different datasets with a monotone missing data structure. The imputation is based on the missing at random (MAR) assumption, i.e., the missing data are assumed to follow the

Neurocrine Biosciences, Inc. Statistical Analysis Plan Study NBI-1065846-MDD2020 16August2023

Status: Approved

same model as the other subjects in their respective treatment arm.

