7.4.1. Sensitivity Analysis of Primary Efficacy Variable

The following sensitivity analysis will be performed for the primary endpoint to explore the robustness of inferences from the main estimator:

• Tipping point analysis (MNAR): The tipping point assumption will be used, i.e., after the first visit with missing data, the trajectories of the subjects in the NBI-1065846 group are assumed to be worse by an amount of delta. After the MI, as defined previously, an amount of delta will be added to each imputed value at Day 57 in the NBI-1065846 group. Successively harsher deltas will be imposed on the imputed values in the NBI-1065846 group, starting with a DARS total score decrease (worsening) of -1. The delta is further decreased in the steps of 1 (ie, -1, -2, -3, ...) until the statistical significance is lost, ie, until the p-value becomes ≥0.1. For the control group, the MI using MAR assumption will be used.

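### The Day 57 efficacy window has no upper limit, so a DARS from the 8-week follow-up visit can be analysed as the observed Day 57 primary value

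*SAP*

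**What the plan says.** **Mapping.** SAP 5.6 states that the nominal visit number for each efficacy visit, "including scheduled and early termination/end of study visits will be re-mapped based on the actual study day according to Table 1". Table 1 has three rows: baseline (Day 1), Day 29 (study days 2 to 43) and Day 57 (study day 44 with no upper bound). Table 2, for safety data, has separate follow-up rows; its Day 106 row starts at "last dose day+43". If several records share a window, "the measurement that is closest to the target study day will be used for the summary tables where one observation per visit is needed".

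**Data collection.** In Protocol Table 8 (Appendix A) the DARS row is marked at screening, Day 1, Day 29, Day 57 or early termination (ET), and Day 106. MADRS and CGI-S are not marked at Day 106. Footnote c sets the timing: "Subjects will return to the clinic approximately 4 and 8 weeks following their final dose for safety follow-up or 7 days (±2"), the last part being for ET assessments. Under Protocol 8.2, subjects who withdraw early and have not withdrawn consent "will be asked to come back for 2 safety follow-up visits at 4 and 8 weeks after last dose of study treatment".

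**Analysis.** SAP 7.3.2 says: "All available assessments up to Day 57 will be used, regardless of occurrence of intercurrent events". SAP 7.4 says: "Subjects who are missing DARS score at Day 57 will have their data imputed through a multiple imputation (MI) procedure". In the tipping-point analysis of SAP 7.4.1, "an amount of delta will be added to each imputed value at Day 57 in the NBI-1065846 group".

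**The concern.** Under Table 1 as written, one follow-up visit gives safety data labelled Day 106 and a DARS labelled Day 57. The closest-to-target rule protects a subject who also has a DARS from Day 44 on that is nearer to Day 57. It does nothing when the follow-up DARS is the only record in the window.

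Such a score is not a Day 57 score. It can be taken weeks late. The restrictions on antidepressant changes and prohibited medication in Protocol 7.1 end at Day 57 or ET, and Table 8 schedules the placebo-control reminder script on Days 1, 29 and 57 only. The treatment policy strategy keeps data collected after intercurrent events, but it does not move the timepoint.

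Whether an exposed subject is observed or imputed for the primary endpoint then depends on which section the programmer follows. That choice also affects:

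- which placebo values inform the control-based imputation;
- who counts as a completer in SAP 7.4.2, where a non-missing Day 57 value is enough;
- how many active-arm values the tipping-point analysis can shift.

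**Working it through.** **Planned missingness.** SAP 3.3 assumes that 85% of 88 subjects complete Day 57, with effect size 0.5 and one-sided alpha 0.1. With 88 × 0.85 / 2 = 37.4 per arm, power = Φ(0.5 × √(37.4/2) − 1.282) = Φ(0.881) = 0.81. The stated figure of about 80% reproduces, and this point does not change it. Subjects without a Day 57 assessment: 0.15 × 88 = 13.2 overall and 0.15 × 44 = 6.6 per arm. This is the upper bound on those exposed.

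**Which records map to Day 57.** ET day = last dose day + 7 (±2). Follow-up day = last dose day + 56 (±3). Dosing days are from Protocol 6.2.

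| Last dose | ET | Window for ET DARS | 8-week follow-up | Record mapped to Day 57 |
|---|---|---|---|---|
| 1 | 8 | Day 29 | 57 (54–60) | follow-up, on target |
| 8 | 15 | Day 29 | 64 (61–67) | follow-up, 7 days late |
| 15 | 22 | Day 29 | 71 (68–74) | follow-up, 14 days late |
| 22 | 29 | Day 29 | 78 (75–81) | follow-up, 21 days late |
| 29 | 36 | Day 29 | 85 (82–88) | follow-up, 28 days late |
| 36 | 43 | Day 29 (Day 57 if ET is on Day 44–45) | 92 (89–95) | follow-up, 35 days late, unless ET is on Day 44–45 |
| 43 | 50 | Day 57 | 99 (96–102) | ET; follow-up (42 days late) only if the ET DARS is missed |
| 50 | 57 | Day 57 | 106 (103–109) | Day 57; follow-up (46–52 days late) only if that DARS is missed |

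**Does SAP 7.3.2 exclude these records?** As a study-day cut, its Day 57 limit removes them. It also removes Day 57 visits held on study days 58 or 59, which Table 8 allows (±2). Read as the Day 57 analysis visit, it takes over Table 1's open window. Neither reading fits the whole plan.

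**Effect on the estimate.** Assume the follow-up score differs from the true Day 57 score by 0.5 SD, in one arm only. With k mapped subjects of 44, the difference moves by k × 0.5 / 44:

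- k = 1: 0.011 SD
- k = 3: 0.034 SD
- k = 7: 0.080 SD

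The sign could go either way.

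**Effect on the tipping point.** The shift per unit of delta is (imputed active subjects) / 44. With 7 imputed it is 7/44 = 0.159. If 3 of those 7 are mapped instead, it is 4/44 = 0.091. The delta at which significance is lost therefore grows by 7/4 = 1.75. As an illustration, assume SD 10, a difference of 4 and the estimate held fixed. SE = 10 × √(2/44) = 2.13 and the margin is 4 − 1.282 × 2.13 = 1.27. The tipping delta is 1.27/0.159, about −8, against 1.27/0.091, about −14. A simulation on the same assumptions (44 per arm, 50 imputations) gave means of −7.2 and −12.7. For a difference of 5 it gave −13.0 and −21.9.

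**Effect on the 9:1 rule (SAP 7.4, Step 2).** With 7 missing, more than 63 retrieved values are needed, which 44 subjects cannot supply under either mapping. One mapped subject changes the outcome only when few are missing, for example from 9/2 = 4.5 to 10/1 = 10.

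**The case against.** The best counter-argument is a third reading of SAP 7.3.2: data up to and including the scheduled Day 57 visit. That keeps study days 58 and 59, excludes the separate safety follow-up period, and has the authority of the text specific to the primary estimand. It is probably what the authors meant. It does not settle the matter, because SAP 5.6 replaces nominal visits with study-day windows for efficacy, so Table 1 would still contradict it. No text gives either section precedence.

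Several narrower objections stand:

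- The closest-to-target rule is worded for summary tables, but SAP 7.4 presents its LS means in summary tables, so the rule can reasonably be read as covering the ANCOVA. Saying so is a clarification only.
- After a last dose on Day 36, an ET visit on Day 44 or 45 protects the subject. After a last dose on Day 1, the follow-up visit falls on target and does no harm.
- Thirteen subjects is a ceiling. Those who stop treatment but attend Day 57 are unaffected, and many who withdraw will not return.
- The 3-of-7 split, SD, differences and 0.5 SD discrepancy are assumptions. Replacing imputed with observed values would also change the estimate, so the 1.75-fold figure isolates one mechanism.
- The shifts for 1 or 3 subjects are about 5% and 16% of one SE (√(2/44) = 0.213 SD). Mapping in both arms would partly cancel if the discrepancies had the same sign.

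These points limit the size of the problem. They do not remove the conflict between the two sections.

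**Conclusion.** The concern holds. Followed as written, Table 1 assigns a wrong Day 57 primary value to any subject whose only DARS from Day 44 on is a late follow-up score, and SAP 7.3.2 does not clearly prevent it. At most about 13 of 88 subjects (about 7 per arm) are exposed, probably fewer; the documents give no count. The effect on the estimate is likely to be modest and its direction is unknown. No loss of power is claimed. The clearer consequence is for the sensitivity analysis: each active-arm subject moved from imputed to observed weakens the delta shift and makes the result look more robust to missing data. Among the efficacy scales visible in Table 8, only the DARS is affected. This should be fixed before unblinding.

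**What to change.** 1. In SAP Table 1, give the Day 57 efficacy window an upper limit. Days 44 to 70 is symmetric about the target (57 ± 13).
2. Add a safety follow-up row (Day 71 onward) and summarise later DARS scores only there.
3. State that a subject with no DARS in the capped window is missing at Day 57 and goes through the SAP 7.4 imputation.
4. Reword SAP 7.3.2 so that data are used to the end of the Day 57 analysis window. This agrees with Table 1 and with the ±2-day visit tolerance.
5. State that the closest-to-target rule also selects the value for the ANCOVA.

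The exact cap is a judgement. At Day 70, follow-up scores after a last dose on Day 1 or 8 (nominal Days 57 and 64) stay in by study day, which fits the treatment policy strategy. Those after a last dose on Day 15 (Days 68 to 74) straddle the limit. If a tighter cap is preferred, 7.3.2 should use the same one.

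The cost is one table row changed, one added and three sentences in the SAP. Trial conduct does not change. A few more subjects may count as missing at Day 57 and be imputed.

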6.2. Study Treatment Administration

Study treatment will be administered orally once weekly (every 7 days \pm 2 days), with each dose taken at least 5 days apart. Subjects receive a loading dose of 160 mg (consisting of four 40 mg tablets) in the clinic on Day 1 (Week 1) and subsequently 80 mg (consisting of two 40 mg tablets) once weekly (Weeks 2 to 8) thereafter. Subjects will also receive their second (Day 8), and fifth (Day 29) doses of study treatment in the clinic. Subjects will take study treatment at home on Days 15, 22, 36, 43, and 50. Study treatment will be administered with 240 mL of water and may be administered with or without food.

If a subject forgets or is unable to take the study treatment, the dose can be taken ± 2 days from the scheduled weekly dose (with each dose taken at least 5 days apart); otherwise the study treatment should be taken at the next dosing time.

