APPENDIX A. SCHEDULE OF ASSESSMENTS

Table 8: Schedule of Assessments

	Screening Period ^a	Treatment Period						Safety Follow-Up Period	
Study Day (Study Week)	Day -28 to Day -1 (W-4 to D-1)	Day 1 ^b Baseline (W1)	Day 8 (±2) (W2)	Day 22 (±2) (W4)	Day 29 (±2) (W5)	Day 43 (±2) (W7)	Day 57 (±2) OR ET Visit	Day 78° (±3) (W12)	Day 106° (±3) (W16)
Visit No.	1	2	3	4	5	6	7	8	9
Onsite Visit	X	X	X		X		X	X	X
Virtual Visit				X		X			
Informed consent	X								
Subject registry database review informed consent	X								
Pharmacogenomic informed consent	X								
Subject registry database review ^d	X								
Inclusion/exclusion criteria	X	update							
Medical history	X	update							
Medication history	X	update							
Physical examination (including height and weight) ^e	X						X	X	X
Triplicate 12-Lead ECG ^f	X	X			X		X		
Vital signs ^g	X	X	X		X		X	X	X
Pregnancy test: Urine (u) Serum (s)	X(s)h	X (u)			X (u)		X (u)	X (u)	X (u)
FSH ⁱ	X								
Clinical laboratory tests	X	X	X		X		X	X	X
Drug/alcohol screen ^j	X	X			X				
Pharmacogenomics sample (optional)		X							
MINI	X								
SAFER Interview	X								
MGH-ATRQ	X								
HAM-D17 ^k	X	X							
PCRS ^k		X			X		X		

	Screening Period ^a	Treatment Period					Safety Follow-Up Period		
Study Day (Study Week)	Day -28 to Day -1 (W-4 to D-1)	Day 1 ^b Baseline (W1)	Day 8 (±2) (W2)	Day 22 (±2) (W4)	Day 29 (±2) (W5)	Day 43 (±2) (W7)	Day 57 (±2) OR ET Visit	Day 78° (±3) (W12)	Day 106° (±3) (W16)
Visit No.	1	2	3	4	5	6	7	8	9
Onsite Visit	X	X	X		X		X	X	X
Virtual Visit				X		X			
SHAPSk	X	X							
DARS ^k	X	X			X		X		X
		X			X		X		
		X			X		X		
					X		X		
		X			X		X		
,1		X					Xc		
MADRS ^k		X			X		X		
CGI-S ^k		X			X		X		
					X		X		
C-SSRS Baseline/Screening Version	X								
C-SSRS Since Last Visit Version		X	X	X	X	X	X	X	X
PK blood sample up to 2 hours predose		X	X		X				
PK blood samples at 0.5-2 hours and 2-36 hours postdose (samples must be obtained ≥30 minutes apart)		X			X				
PK blood sample at any time ^m							X		
Dispense ⁿ /Collect ^o study treatment		Xn	X ⁿ				Xº		
Dose study treatment ^p				X (once	weekly) ^p				
Remind subjects to take study treatment ^p				X (once	weekly) ^p				
Compliance check ^q		X	X	X	X	X			

	Screening Period ^a		Safety Follow-U						
Study Day (Study Week)	Day -28 to Day -1 (W-4 to D-1)	Day 1 ^b Baseline (W1)	Day 8 (±2) (W2)	Day 22 (±2) (W4)	Day 29 (±2) (W5)	Day 43 (±2) (W7)	Day 57 (±2) OR ET Visit	Day 78° (±3) (W12)	Day 106° (±3) (W16)
Visit No.	1	2	3	4	5	6	7	8	9
Onsite Visit	X	X	X		X		X	X	X

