9.4. Laboratory Safety Parameters

The hematology and clinical chemistry will be summarized with descriptive statistics by treatment at baseline and at each scheduled postbaseline visit through follow-up visit (Day 106). Both observed values and changes from baseline will be summarized by treatment group.

Shift tables from baseline to Day 57 will be presented for selected clinical laboratory variables based on the reference range-based categories of "Low," "Normal," or "High." A clinical laboratory variable value will be assigned to one of these three categories according to the reference ranges provided by the central clinical laboratory. The shift table will have rows reflecting the reference range category at baseline, and columns reflecting the reference range category on Day 57. A "Total" row and "Total" column will also be included. The number of subjects in each shift category will be displayed in the table.

The shift table will be presented by treatment group for the following clinical laboratory variables:

- aspartate aminotransferase (AST),
- alanine aminotransferase (ALT),
- alkaline phosphatase (ALP),
- gamma-glutamyl transferase (GGT),
- total bilirubin,
- creatine kinase,
- creatinine,
- blood urea nitrogen (BUN),
- white blood cell count,

Neurocrine Biosciences, Inc. Statistical Analysis Plan Study NBI-1065846-MDD2020 16August2023

- absolute neutrophil count,
- hemoglobin,
- platelet count,

Repeat clinical laboratory samples may be collected at any time during this study due to either missing or abnormal results. The general rule for summarizing these data is to include the original sample results in summary tables. Exceptions to this rule is that if there are missing results from the original lab samples at screening, the results of a repeat screening sample will be substituted for the missing results in summary tables.

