9.6. Body Weight

The body weight data (in units of kilograms) will be summarized with descriptive statistics by treatment group at baseline and at each scheduled postbaseline visit through follow-up visit. Observed values and absolute and percent changes from baseline will be summarized.

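### The safety Day 57 window closes on the last dose day (about Day 50), so no on-schedule Day 57 visit can fall in it and its data go to a follow-up row

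*SAP*

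**What the plan says.** SAP Section 5.6 re-maps all safety visits to analysis visits through Table 2. Scheduled, unscheduled, repeat and early termination (ET) visits are all included, so a scheduled visit does not keep its nominal label.

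- The Day 57 row has target Day 57 and window "51-last dose day".
- The Day 78 row has its target at last dose day+28 and window "Last dose day+1-last dose day+42".
- The Day 106 row starts at last dose day+43.
- When several values share a row, "the measurement that is closest to the target study day will be used for the summary tables where one observation per visit is needed".

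On dosing, Protocol Section 6.2 states: "Subjects will take study treatment at home on Days 15, 22, 36, 43, and 50". Each dose may move by 2 days either way. Protocol Appendix A, Table 8, heads the end-of-treatment column "Day 57 (±2) OR ET Visit".

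Several outputs use the Day 57 row. SAP Section 9.4 says: "Shift tables from baseline to Day 57 will be presented for selected clinical laboratory variables". The same section, with Sections 9.5 and 9.7, plans summaries by scheduled visit for laboratory values, vital signs and ECG. Section 9.6 says: "The body weight data (in units of kilograms) will be summarized with descriptive statistics by treatment group at baseline", and then at each later scheduled visit.

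**The concern.** The Day 57 visit comes about a week after the last dose, but its safety window stops on the day of that dose. The row therefore excludes the visit it is named after, and the next row, which starts the day after the last dose, takes the data instead.

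The end-of-treatment time point is at stake across the by-visit safety tables:

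- **Laboratory.** The only planned laboratory shift tables run from baseline to Day 57. They cover AST, ALT, ALP, GGT, total bilirubin, creatine kinase, creatinine, BUN and blood counts. Protocol Section 2.2 singles out hepatobiliary injury for monitoring, and SAP Section 9.4 plans no worst-value laboratory summary as a backstop. After Day 1, Treatment Period laboratory tests are scheduled only on Days 8, 29 and 57, so without Day 57 the last scheduled Treatment Period row with laboratory data is Day 29.
- **Weight.** Table 8 schedules it at screening and Days 57, 78 and 106 only. Its single scheduled Treatment Period value loses its row.
- **ECG.** Footnote f of Table 8 requires ECGs on Days 78 and 106 only after an abnormal Treatment Period ECG. For a subject with no Day 78 ECG, the Day 57 ECG is the value left in the Day 78 row and is reported there.

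A second problem concerns subjects who stop drug early. For them the last-dose-based rows overlap the fixed-day rows, and the SAP does not say which takes priority.

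**Working it through.** **Inputs.** Weekly dosing from Day 1, eight doses, each ±2 days (Protocol 6.2). Day 57 visit ±2 days, so Days 55-59; Day 78 visit ±3 days, so Days 75-81; ET visit 7±2 days after the final dose (Protocol Table 8 and footnote c). Windows and targets from SAP Table 2. Let L be the last dose day and v the visit day.

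**1. Reproduce the plan's own days.** The eighth dose is on Day 1 + 7×7 = 50. Then 50 + 28 = 78 and 50 + 56 = 106, which match the nominal follow-up days. Table 2's own targets therefore assume a last dose on Day 50.

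**2. Day 57 window, Day 51 to L.**

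| Last dose day L | Day 57 window | Day 78 window (L+1 to L+42) |
|---|---|---|
| 48 | empty | 49-90 |
| 49 | empty | 50-91 |
| 50 | empty | 51-92 |
| 51 | 51 only | 52-93 |
| 52 | 51-52 | 53-94 |

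A visit on day v enters the Day 57 row only if 51 ≤ v ≤ L. The earliest permitted visit is Day 55, so L would have to be at least 55. The latest permitted last dose is Day 52.

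**3. On-schedule completers.** Five last dose days × five visit days = 25 combinations. In the Day 57 row: 0 of 25. In the Day 78 row, and no other: 25 of 25.

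**4. Competition within the Day 78 row.** The target L+28 runs from Day 76 to Day 80. Distance of the Day 57 visit from the target: from 76 − 59 = 17 to 80 − 55 = 25 days. Distance of a Day 78 visit on Days 75-81: from 0 to 5 days (80 − 75 = 5; 81 − 76 = 5). The Day 78 visit is closer in all 5×5×7 = 175 combinations. The Day 57 value is dropped where a Day 78 value exists and shown as Day 78 where none does.

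**5. All permitted last dose days.** Day 1, plus seven later doses × 5 days each, gives 36 days. With five visit days that makes 180 combinations: 0 in the Day 57 row, 140 in Day 78 and 40 in Day 106. Subjects who stop drug early but attend Day 57 are therefore missed as well.

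**6. Overlap for early stoppers.** Take last doses on Days 1, 8, 15, 22, 29, 36 and 43, with the ET visit at L+5 to L+9: 7×5 = 35 combinations. Of these, 33 fall in two rows. The other two (L = 43, ET on Day 51 or 52) fall in Day 78 only. Example: with L = 22, an ET visit on Day 29 fits both the Day 29 row (26-36) and the Day 78 row (23-64). A Day 57 visit by the same subject is at L+35 and maps to Day 78.

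**7. Subjects concerned.** Protocol Section 11.2 expects 85% of 88 to complete Day 57: 0.85 × 88 = 74.8, about 75 subjects. The figures in steps 3 to 6 count combinations and are not subject frequencies.

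**The case against.** The strongest objection is to severity. Safety output is descriptive, with no hypothesis test (SAP Section 9). AE tables, highest-value QTcF categories, the all-postbaseline C-SSRS summary, the efficacy analyses and subject-level liver monitoring do not depend on this row. The intent is plain, and a near-empty shift table would be noticed at the first table run. That limits the harm, but it does not make the window correct. A Day 57 ECG shown as Day 78 is much harder to notice. SAP Section 1 also says that analysis decisions are settled and documented before lock and unblinding, and an unwritten correction by a programmer would not meet that.

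Dosing drift is a possible way out. If intervals of up to 9 days could accumulate, the last dose might reach Day 1 + 9×7 = 64. The protocol's fixed dosing days, and its ±2 days counted from the scheduled dose, rule that reading out.

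It can also be said that a subject has either an ET visit or a Day 57 visit. Table 8 gives them one column, and Protocol Sections 4.1 and 8.2 tie the ET visit to withdrawal from the study. But footnotes c and m and Section 9.2.2.1 also attach it to stopping treatment, while Sections 4.1 and 8.1 keep such subjects in the study. The text is not consistent, so both visits are possible rather than certain. The empty Day 57 row does not depend on this.

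Finally, two corner cases deserve a sentence in the SAP. Protocol Section 8.2 allows an ET visit more than 3 weeks after the last dose to replace the 4-week follow-up. For early stoppers, a follow-up visit can also coincide with a Treatment Period visit.

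**Conclusion.** The concern holds, with high confidence, and must be fixed. Read as written, Table 2 sends no on-schedule Day 57 visit to the Day 57 safety row: 0 of 25 combinations for completers and 0 of 180 over all permitted last dose days. For completers, every such visit goes to the Day 78 row. The Day 57 laboratory shift tables and the end-of-treatment laboratory, vital sign and weight rows lose their data, and some Day 57 ECGs are reported under a follow-up label. The documents do not give the proportion of subjects without a Day 78 ECG.

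This rests on doses within ±2 days of the scheduled day, visits on Days 55-59, and Table 2 applied literally to scheduled visits, as Section 5.6 directs. It is an error in what the safety tables contain. It does not affect subject protection or the primary result.

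**What to change.** Change SAP Table 2 as follows.

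1. Map every Treatment Period visit by fixed study-day windows, including both the ET and the Day 57 visit when a subject has both. Run the Day 57 row from Day 51 onward, with no upper bound at the last dose day.
2. Apply the last-dose-based rows (Day 78: last dose day+1 to +42; Day 106: last dose day+43 onward) only to nominal Visits 8 and 9, whenever they occur, and to unscheduled or repeat assessments after the later of the subject's ET and Day 57 visits. If the subject has neither visit, use assessments after Day 59.
3. Map all other unscheduled or repeat assessments by the fixed windows.
4. State that a visit coinciding with a follow-up is mapped by its recorded nominal visit, and say how a late ET visit is shown. As drafted here, it takes its fixed-window row. Whether values taken well after the last dose should be flagged in the Day 57 row is for the sponsor to state.

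Checked against the permitted days, these rules give every Day 57 visit on Days 55-59 the Day 57 row. That includes all 775 combinations with both visits (31 last dose days up to Day 45 × 5 ET days × 5 visit days), and in each of these the ET visit maps to one row. On-time Visits 8 and 9 map to Days 78 and 106 for all 36 last dose days, even when Visit 8 falls before Day 57.

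The cost is a SAP table edit and its programming before database lock. No new data are needed, and no trial procedure changes.
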